4.1.3 Definition of Dose-Limiting Toxicity

A dose-limiting toxicity (DLT) is defined as any AE occurring in Cycle 1 that fulfills one or more of the following criteria. Toxicities will be graded and documented according to the NCI CTCAE, version 4.03 guidelines (see Appendix 4):

- Nonhematological Grade 3 or greater toxicity that is unrelated to underlying disease, occurring in Cycle 1 with the following exceptions:
 - Alopecia
 - o Grade 3 nausea, vomiting, diarrhea or rash lasting less than 72 hours (with optimal medical management)
 - o Grade 3 QTcF prolongation that is < 40 msec increase over baseline in a patient with a bundle branch block (BBB)
 - Grade 3 or 4 toxicity determined to be a sign or symptom of differentiation syndrome that resolves/responds to treatment interventions to < Grade 3 within 7 days (see Section 5.5.1)
- Any Grade 3 non-hematologic laboratory finding, unrelated to underlying disease, occurring in Cycle 1
- Hematologic Grade 4 toxicity as defined by CTCAE on Day 42, in the absence of disease
- Inability to tolerate a minimum of 75% of FT-2102 scheduled doses during Cycle 1 due to an AE. This applies to patients who have their dose held due to AEs per Section 6.8.1.

All patients will be monitored for bone marrow function throughout the study, but these findings may not be considered a DLT unless they fulfill the above criteria.

A DLT is defined within the 28 days of Cycle 1. However, the sponsor will evaluate all safety data, on an ongoing basis, beyond Cycle 1 for determination of an appropriate dose for Phase 2 or later trials.

4.1.4 Phase 1 Dose-Expansion Stage

The following expansion cohorts are proposed:

- 1. SA FT-2102 at the MTD or MED in patients with relapsed or refractory (R/R) AML or MDS
- 2. SA FT-2102 at a dose less than the MTD or MED (only if MTD or MED > 150 mg QD) in patients with R/R AML or MDS

- 3. Combination FT-2102 (MTD or MED) + azacitidine in patients with AML or MDS with no prior anti-AML/MDS therapy
- 4. Combination FT-2102 (MTD or MED) + azacitidine in patients with AML or MDS that is R/R to prior anti-AML/MDS therapy (including hypomethylating therapies)

Patients will continue to be monitored for safety while on study treatment and for up to 28 days after treatment discontinuation (last dose of study drug) or until resolution or stabilization of AEs, except for patients who withdraw consent. Patients will also be monitored for evidence of antileukemic or antimyelodysplastic activity (Section 4.3).

Patients participating in the dose-expansion cohorts may be followed for survival for up to 12 months from C1D1 or for 28 days after treatment discontinuation (whichever is longer).

FT-2102 in combination with cytarabine:

After dose-expansion is complete for FT-2102 as a single agent and FT-2102 in combination with azacitidine, a cohort of 6 patients with AML harboring IDH1 mutation will be treated with FT-2102 in combination with cytarabine 20 mg BID for 10 days, and then cytarabine will be stopped for 18 days. FT-2102 will be given in accordance with dosing schedule × 28 days out of 28 days. The starting dose of FT-2102 will be 150 mg BID. Further dose-escalation of FT-2102 in combination with cytarabine will not occur beyond 150 mg BID.

If \geq 1 DLTs are observed at the 150 mg BID dose in combination with cytarabine, a lower dose level of FT-2102 may be explored.

4.2 Phase 2 Stage

Specific populations of patients with AML/MDS harboring IDH1-R132 mutations will be enrolled to further characterize the safety and efficacy of FT-2102 at the RP2D in Phase 2 cohorts. Only 1 dose level of FT-2102 as SA and 1 dose level of FT-2102 in combination with azacitidine will be evaluated in the proposed Phase 2 cohorts.

FT-2102 150 mg BID is the RP2D (see Section 1.5.1). This RP2D has been confirmed for SA and azacitidine combination treatment.

Phase 2 cohorts may include the following:

Single-Agent Cohorts:

Cohort 1 (SA FT-2102): approximately 173 evaluable patients with R/R AML. To account for discordance between local and central mutation testing, approximately 190 patients may be enrolled into this cohort to obtain 173 evaluable patients.

Cohort 2 (SA FT-2102): approximately 53 patients with AML in morphologic CR/CRi after prior therapy (+/- HSCT) with residual IDH1-R132 mutation ($\geq 0.01\%$) detected in the bone marrow.

Cohort 3 (SA FT-2102): approximately 20 patients with R/R AML/MDS that have been previously treated with FT-2102. Patients who undergo HSCT on-study then relapse post-HSCT are allowed in this cohort.

Azacitidine Combination Cohorts:

Cohort 4 (FT-2102 in combination with azacitidine): approximately 20 patients with R/R AML/MDS that is naïve to prior hypomethylating therapy and IDH1 inhibitor therapy.

Cohort 5 (FT-2102 in combination with azacitidine): approximately 20 patients with R/R AML/MDS that have inadequately responded to or have progressed on prior hypomethylating therapy.

Cohort 6 (FT-2102 in combination with azacitidine): approximately 44 patients with R/R AML/MDS that have been previously treated with SA FT-2102 as their last therapy prior to study enrollment. The actual number of patients in this cohort may be larger, since patients from the FT-2102 SA cohorts of this study are allowed to be enrolled in Cohort 6 after their disease progression.

Treatment Naïve Cohorts:

Cohort 7 (SA FT-2102): Approximately 54 treatment naïve AML patients for whom standard treatments are contraindicated.

Cohort 8 (FT-2102 in combination with azacitidine): Approximately 28 treatment naïve AML patients who are candidates for azacitidine as a first line treatment.

Note for Phase 2 Cohort 7 and Phase 2 Cohort 8: Treatment naïve is defined as no prior treatment for AML. Patients may have received a prior treatment for another hematologic malignancy.

Patients will be monitored for safety while on study treatment and for up to 28 days after treatment discontinuation (last dose of study drug) or until resolution or stabilization of AEs, except for patients who withdraw consent.

4.3 Response Assessment

All patients participating in this study will undergo response assessments through evaluation of clinical findings and bone marrow/peripheral blood cell counts and morphology. Criteria to guide the investigator's assessment of response are defined in Table 3 below and Appendix 7 and Appendix 8.

Bone marrow for response assessment is required at:

C2D1 if no peripheral blasts; otherwise, at C3D1, regardless of peripheral blast count
 Not applicable for patients enrolled after Protocol Version 7/ Amendment 6

- For patients with AML, every 6 cycles thereafter unless there is a suspicion of relapse/progression
- For patients with MDS, to be performed as clinically indicated
- When progressive disease is suspected
- The same assessment frequency should carry on post-HSCT
- For Phase 2 Cohort 2 only: bone marrow assessment should be done at C2D1, C4D1, C6D1, and only if relapse is suspected thereafter

Response criteria are derived from the International Working Group (IWG) response criteria for AML (2003) and MDS (2006) where applicable; refer also to Stein et al. 2017.

In general, HSCT is not considered an event in time to event analyses. Patients who stop treatment with FT-2102 to have HSCT will continue to be monitored for duration of response. HSCT is not considered an anti-leukemia therapy for purposes of analyses described herein.

 Table 3
 Response Assessment Criteria

Per Protocol Response Criterion ^{a,b}	Corresponding IWG Response/ Modified Response Criteria		
-	AML (2003)	MDS (2006)	
Morphologic Complete Remission	CR°	CR	
CR with partial hematologic recovery	CRh	Not applicable	
CR with incomplete blood count recovery	CRi	Marrow CR	
Morphologic leukemia-free state	MLFS	Not applicable	
Partial Response	PR	PR	
Stable Disease ^d	Stable Disease ^d	Stable Disease	
Treatment Failure	Progressive disease (PD) e /Relapse	Relapse /PD	

AML = acute myelogenous leukemia; CR = complete remission; CRh = complete response with partial hematologic recovery; CRi = complete remission with incomplete blood count recovery; MLFS = morphologic leukemia-free state; PD = progressive disease; PR = partial response.

Source: Cheson et al. 2003; Cheson et al. 2006; Stein et al. 2017

- Additional response criteria per IWG (e.g., cytogenetic or molecular complete remission) may be collected when available or provided. However, investigators will be asked to provide response assessment corresponding to the per protocol response criteria outlined.
- For MDS, responses must last at least 4 weeks (i.e., confirmation required at 4 weeks) and hematologic improvements (HI) must last at least 8 weeks. For AML, no minimum duration of response required to qualify for a given response.
- The assessment frequency for CR should also be applied to patients in CRm and CRc. Please refer to Appendix 7 for definitions.
- d Stable Disease (SD) is defined as failure to achieve a partial response but not meeting criteria for progressive disease. SD lasting for a period of more than 8 weeks is considered clinical benefit
- Progressive disease (PD) in AML is defined as previously having demonstrated partial remission or stable disease. For those with 5% to 66% bone marrow blasts at nadir, a > 50% increase in bone marrow blast count percentage from the nadir and percentage is \geq 20%; and for patients with \geq 67% bone marrow blasts at nadir, a doubling of the nadir absolute peripheral blood blast count with a final absolute peripheral blood blast count > 10×10^9 /L

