6.1.22 Cycle 5 and Beyond, Day 1 (Every Other Cycle)

Beginning with Cycle 5, patients will return to the clinic every other cycle.

All procedures to be performed predose:

- Concomitant medication assessment
- Weight
- Vital signs (temperature, blood pressure, pulse rate, and respiratory rate)
- 12-lead ECG as clinically indicated
- ECOG performance status
- Symptom-directed physical examination
- Serum or urine pregnancy test for female patients of childbearing potential
- Clinical serum chemistries
- CBC with differential and platelet count
- Bone marrow aspirate or biopsy for response assessment
 - o For patients with AML: Every 6 cycles unless there is an indication of relapse/progression
 - o For patients with MDS: As clinically indicated
 - o For patients enrolled in Phase 2 Cohort 2: Only if there is a suspicion of relapse
- AE monitoring

Cycle 5 and beyond (every other cycle): Day 1 testing may be done within 72 hours prior to the Day 1 visit.

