Response assessments will be performed through evaluation of clinical findings and bone marrow/peripheral blood cell counts and morphology. Response criteria are derived from the International Working Group (IWG) response criteria for AML (Cheson et al. 2003) and MDS (Cheson et al. 2006) where applicable, and Stein et al. 2017, as outlined in the protocol section 4.3, Appendix 6 and Appendix 7.

Bone marrow for response assessment is required:

- at C2D1 if no peripheral blasts; otherwise, at C3D1, regardless of peripheral blast count;
- at least every 2 cycles (4 to 8 weeks) until morphologic complete remission (CR) is achieved, then up to every 3 cycles (for duration of response assessment) for 12 months after CR achievement, then up to every 6 cycles thereafter;
- when progressive disease is suspected;
- for Phase 2 Cohort 2 only: at C2D1, C4D1, C6D1 and every 6 cycles thereafter.

Response assessment requirements and frequency are the same for all subjects, including those that discontinue treatment due to hematopoietic stem cell transplant (HSCT).

In general, HSCT is not considered an event in time to event analyses. Patients who stop treatment with FT-2102 to have HSCT will continue to be monitored for duration of

response. HSCT is not considered an anti-leukemia therapy for purposes of analyses described herein.

In general, for the purposes of statistical analyses, relapse, progressive disease (PD), or disease progression will be treated interchangeably as being indicative of disease worsening.

AML Response: Following responses for AML will be evaluated by investigator based on the modified Cheson criteria (Cheson et al. 2003). Best overall response for each patient is selected based on the highest category achieved on study from the ordered list in the table below:

		Complete	Overall
Investigator Assessment of AML Response	CR/CRh	Response	Response
Molecular CR (CRm)		$\overline{\mathbf{v}}$	$\overline{\mathbf{v}}$
Cytogenetic CR (CRc)			
Complete Remission (CR)			
CR with Partial Hematologic Recovery (CRh)			
CR with incomplete recovery (CRi)			
Morphologic leukemia-free state (MLFS)			
Partial Remission (PR)			
Clinical Benefit			
Stable Disease			
Resistant Disease			
Relapse			
Progressive Disease (PD)			
Not Evaluable			
Not Done			

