Since this study was ongoing during the COVID-19 pandemic, a sensitivity analysis will be performed on OS, DCR, DCR/CRh, and DOR in which patients who have died due to COVID-19 will be censored to assess the effect that COVID-19 had on time to event endpoints.

4-Month Relapse-Free Survival (RFS) Rate: The primary endpoint for Phase 2 Cohort 2 AML patients is the 4-Month RFS rate. This will be evaluated by a Simon 2-Stage design described in Section IV.C, testing the null hypothesis that the 4-month RFS rate is < 80%. It is defined as the proportion of patients in Phase 2 Cohort 2 who have not relapsed or died on or before their 4-month response evaluation. If a patient does not receive a disease response assessment at their 4-month visit but has a subsequent disease response assessment on or after study day 120 that shows non-progression/ non-relapse, they will be evaluated as having achieved 4-month RFS. This rate is not calculated for MDS patients, or for AML patients in any other cohort.

Relapse-Free Survival (RFS): RFS will be calculated for all patients in Phase 2 Cohort 2, who are patients who have achieved a response of CRi or better. It is the time in months between the date of first dose until relapse, start of other (non-protocol study drug) new antileukemia therapy, or death from any cause, whichever occurs first. Hematopoietic stem cell transplant (HSCT) is not considered an event for RFS. For a patient who is responding and experiences none of these events before the end of study follow up, RFS will be censored as per Table 1. The percentage of patients with RFS will be estimated at landmark timepoints.

Event-free survival (EFS): EFS is defined as the time in months between first dose of study drug and disease progression, relapse, death from any cause, treatment failure, or start of other (non-protocol study drug) new antileukemia therapy, whichever occurs first. HSCT is not an event for EFS, and patients experiencing HSCT will continue to be followed until an event occurs. For EFS, treatment failure will be operationally defined as not achieving a best

overall response of CR, CRh, or CRi on study. The date of treatment failure for patients with this event will be the date of the last response assessment while on study.

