RFS, EFS, OS, TTCR/CRh, TTCR, TTR, DCR/CRh, DCR, DOR: Time to event endpoints listed here will be expressed as the number of months from first dose to the event and will be analyzed using Kaplan-Meier (KM) methods for each cohort, with the exception of TTCR/CRh, TTCR, and TTR, since these analyses are performed only on the subset of responders and censoring is unnecessary. The analysis will include median, 1st and 3rd quartiles for time calculated using Kaplan-Meier methods, and the 95% confidence interval for the median

calculated using the Brookmeyer-Crowley method. The estimated probability of survival over time for RFS, EFS, OS, DCR/CRh, DCR, and DOR will be plotted as KM curves for Phase 2 Cohort 1, with the exception of RFS, which will be performed for Phase 2 Cohort 2 only. Appendix 2 provides the SAS code.

The survival probability and 95% confidence interval will be estimated at selected landmark timepoints of: 3 months, 6 months, 12 months, and 24 months based on Kaplan-Meier product-limit method and Greenwood's formula. A month will be calculated as time in days divided by 30.4375.

Table 1. Censoring Rules

Case	Censoring Rule
Patient has no post baseline assessments	Censor at date of first dose
and no date of death recorded	
Patient did not die or experience PD or	Censor at date of last adequate response
relapse*	assessment (any response assessment that is
	not "Not Evaluable" or "Not Done")
Patient in Phase 1 started on single agent	Censor at date of last adequate response
therapy, but switched to combination	assessment prior to the combination therapy
therapy	

*For patients who discontinue FT-2102 treatment to receive HSCT and remain on study to be followed until documented disease relapse, confirmation of relapse is not required in this situation, and a single occurrence of relapse will be considered as documented "confirmed" relapse in analyses of response.

The following sensitivity analyses of DCR/CRh will be performed with censoring rule variations in EE patients:

- 1. Patients who undergo HSCT will be censored at the last adequate assessment prior to HSCT
- 2. Patients who discontinued study treatment due to undocumented progression will be considered as events at the date of last dose
- 3. Patients with subsequent anti-cancer therapies prior to an event date will be considered to be censored the day before the start of the anti-cancer therapy.

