- 4. Patients with subsequent anti-cancer therapies prior to an event date will be considered as having an event as the start of the anti-cancer therapy.
- 5. Patients who didn't have an event and are still on treatment will be censored at the last treatment date, otherwise will be censored at the last response assessment.

For DOR and DCR HSCT sensitivity analysis will be performed, where patients who undergo HSCT will be censored at the last adequate assessment prior to HSCT. The following subgroup analyses will be performed:

• CR/CRh rate, ORR, DCR/CRh – For AML patients in the EE analysis set: AML type (primary or secondary), disease state (relapsed/refractory or treatment naive), AML cytogenetic risk classification, IDH1 mutation type, IDH1 mutation confirmed by

central lab, age group, sex, region, race, baseline ECOG PS, prior HSCT for AML, prior HMA, prior IDH1 therapy, and prior FT-2102 therapy.

• OS, EFS – For AML patients in the FAS analysis set: AML type (primary or secondary), disease state (relapsed/refractory or treatment naive), AML cytogenetic risk classification, IDH1 mutation type, IDH1 mutation confirmed by central lab, age group, sex, region, race, baseline ECOG PS, prior HSCT for AML, prior HMA, prior IDH1 therapy, and prior FT-2102 therapy.

Kaplan Meier plots will not be produced for subgroup analyses.

Transfusion Independence

Transfusion independence will be analyzed as part of the clinical benefit expected from FT-2102. The percentage of patients who are transfusion dependent at baseline will be summarized (overall and by type of blood product of RBC and/or platelets). The proportion of patients who became transfusion independent during any 28-day and 56-day period during treatment will be summarized by best overall response on study. Percentages will be based on the number of patients within the best overall response category.

Swim Lane Plot of Time on Treatment and Duration of Response

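### Cohort 2 relapse-free survival (RFS) at 12 and 24 months can be biased downward: the SAP censors at the last adequate response assessment, but the current protocol schedules no marrow after C6D1

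*Protocol*

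**What the plan says.** **Marrow schedule, protocol.** Section 4.3 states for Cohort 2: "bone marrow assessment should be done at C2D1, C4D1, C6D1, and only if relapse is suspected thereafter". Section 6.1.22, which covers Cycle 5 onward, states: "For patients enrolled in Phase 2 Cohort 2: Only if there is a suspicion of relapse". It makes no exception for C6D1, and its every-other-cycle visits from Cycle 5 do not fall on C6D1.

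**Marrow schedule, SAP.** Section XI.A requires marrow "for Phase 2 Cohort 2 only: at C2D1, C4D1, C6D1 and every 6 cycles thereafter". The Appendix 1 footnote adds C12D1 and then every 6 cycles. The SAP Introduction says the plan rests on protocol version 5. Protocol 6.1 introduces a reduced schedule of events with Version 7/Amendment 6.

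**Censoring.** SAP XI.A says of a responding patient with no event that "RFS will be censored as per Table 1". Table 1 in XI.B tells the analyst: "Censor at date of last adequate response" assessment. It excludes only assessments recorded as Not Evaluable or Not Done.

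**Reporting.** RFS is analysed by Kaplan-Meier, with estimates at "selected landmark timepoints of: 3 months, 6 months, 12 months, and 24 months". Relapse, death and new antileukemia therapy are events.

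**Nearest safeguard.** The fifth DCR/CRh sensitivity analysis says: "Patients who didn't have an event and are still on treatment will be censored at the last treatment date". It covers efficacy-evaluable (EE) patients only. The EE set is confined to Cohort 1 and is used only at the second interim analysis.

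**The concern.** The censoring rule suits a schedule with regular marrows, as in the SAP. It fits poorly once routine marrows stop.

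Events and non-events are then documented unequally. Under Protocol Appendix 7, relapse can be called on peripheral blasts or extramedullary disease, and suspicion triggers a marrow. Deaths and new therapy can be picked up at the roughly three-monthly survival contacts (Protocol 6.1.26). Continued remission requires marrow blasts below 5%, and after C6D1 no marrow is scheduled to show it.

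If a response is recorded only when a marrow is done, event-free patients are censored at about C6D1, and those who later have an event stay in the risk set until it happens. Censoring then depends on outcome. The late part of the RFS curve, and the 12- and 24-month landmarks read from it, would understate how long remissions last. RFS over time is a secondary endpoint for Cohort 2, and no sensitivity analysis covers this.

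**Working it through.** **The plan's own figure.** Cohort 2 stops if 9 or fewer of 11 patients are relapse-free at 4 months, and otherwise rejects the null with 48 or more of 53. An exact two-stage binomial calculation gives a one-sided type I error of 0.0248 at 80% and power of 0.805 at 94%. The stated 0.025 and 80% are reproduced. The same two rates are used below.

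**Inputs from the documents.** N = 53; 4-month RFS of 94% or 80%; 28-day cycles, so C6D1 is Day 5 × 28 + 1 = 141; 141/30.4375 = 4.63 months; the Table 1 censoring rule.

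**Assumptions.** RFS is exponential. Follow-up is uniform over 12–36 months, uniform over 24–36 months, or 36 months for all. The documents give 36 months only as a maximum for survival follow-up. In the worst case every patient is on the Protocol 4.3 schedule and only a marrow counts as an assessment.

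**Closed form.** With common follow-up F and c = 4.63 months, the risk set after c holds only patients whose event falls between c and F. Kaplan-Meier then estimates

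S(c) × [S(t) − S(F)] / [S(c) − S(F)].

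At 94% and F = 36: S(c) = 0.931, S(12) = 0.831, S(24) = 0.690, S(36) = 0.573.

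- 12 months: 0.931 × (0.831 − 0.573)/(0.931 − 0.573) = 0.67, against 0.83.
- 24 months: 0.931 × (0.690 − 0.573)/(0.931 − 0.573) = 0.30, against 0.69.

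**Simulation, worst case** (600 cohorts of 53 per setting):

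| 4-month RFS | Follow-up (months) | 6 months | 12 months | 24 months |
|---|---|---|---|---|
| 94% | true value | 0.911 | 0.831 | 0.690 |
| | 12–36 | 0.858 | 0.547 | 0.111 |
| | 24–36 | 0.874 | 0.616 | 0.187 |
| | 36 | 0.884 | 0.673 | 0.307 |
| 80% | true value | 0.716 | 0.512 | 0.262 |
| | 12–36 | 0.681 | 0.357 | 0.056 |
| | 24–36 | 0.704 | 0.427 | 0.095 |
| | 36 | 0.705 | 0.457 | 0.152 |

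In the 94% case the number at risk at 6 months falls from about 48 to between 12 and 18.

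**If some patients have later assessments.** Let a share q of event-free patients be assessed to the end of follow-up. The closed form becomes

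S(c) × [S(t) − (1 − q)S(F)] / [S(c) − (1 − q)S(F)].

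At 94%, F = 36 and q = 0.5, so that (1 − q)S(F) = 0.2865:

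- 12 months: 0.931 × (0.831 − 0.2865)/(0.931 − 0.2865) = 0.79.
- 24 months: 0.931 × (0.690 − 0.2865)/(0.931 − 0.2865) = 0.58.

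Simulations with half the patients assessed later give 0.55 to 0.59 at 24 months, which is 10 to 14 points low.

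**If the rule and schedule match.** At 94%, with marrow every 6 cycles after C6D1, the simulated values are 0.825–0.832 at 12 months and 0.655–0.691 at 24 months. With the every-other-cycle visits counted as response assessments they are 0.829–0.831 and 0.679–0.691, within about 1 point of the truth.

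**The case against.** A reader might infer that every Cohort 2 patient in remission certainly leaves the risk set at Day 141, that all later landmarks including 6 months are sharply wrong, and that 24-month RFS could fall to zero. The documents do not support that.

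- **An adequate assessment is not limited to a marrow.** Protocol 4.3 and SAP XI.A describe response assessment through clinical findings together with marrow and peripheral blood. Blood counts with differential and a symptom-directed examination continue every other cycle from Cycle 5.
- **Some patients may have later marrows.** The SAP carries marrow every 6 cycles from protocol version 5, so patients followed under that schedule could have marrows after Day 141. Protocol Appendix 2, for later enrollees, also says every 6 cycles with no Cohort 2 exception, though it refers back to Section 4.3. A negative marrow done on suspicion, or an end-of-treatment marrow, would also move a censoring date later.
- **The size depends on the landmark and on follow-up.** The 6-month bias is only about 1 to 5 points in the worst case. A 24-month estimate of zero arises only if every patient's follow-up is assumed to end at 24 months.
- **The endpoint is secondary and descriptive.** No decision rule hangs on it.

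All of this stands, and it makes the size conditional. It does not remove the problem. Protocol 6.3 ties the on-treatment marrow to the response assessment, and nothing says that a blood-count visit produces a recorded response. The SAP leaves undefined the term on which the result turns.

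**Conclusion.** The concern holds in conditional form. The SAP's censoring rule was written for a marrow schedule that the current protocol no longer has. To the extent that only marrow-based assessments are recorded as responses, Cohort 2 RFS at 12 and 24 months is biased downward.

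The worst-case loss at 94% is about 16 to 28 points at 12 months and 38 to 58 points at 24 months. At 80% it is about 6 to 16 and 11 to 21 points. These figures rest on exponential RFS, assumed follow-up, all patients on the current schedule and the marrow-only reading. The real mix of schedules and the recording practice are unknown, so they are an upper range and not a forecast.

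The 4-month primary rate is a simple proportion that Table 1 does not touch. The marrow schedules in Protocol 4.3, Protocol 6.1.22, SAP XI.A and SAP Appendix 1 also disagree, including on whether C6D1 itself is scheduled.

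**What to change.** 1. In SAP Table 1, add a rule for Cohort 2 RFS: censor event-free patients at the last visit or disease follow-up contact at which relapse was neither documented nor suspected, based on clinical evaluation and blood count with differential. State whether such a visit is an adequate response assessment.
2. Present censoring at the last marrow-based assessment as a sensitivity analysis.
3. If the present rule is kept as the main analysis, report no RFS landmark beyond the last scheduled marrow.
4. Reconcile the Cohort 2 marrow schedules in Protocol 4.3 and 6.1.22 and in SAP XI.A and Appendix 1.

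The cost is SAP wording and one derivation, and the SAP allows changes until database lock. The visits are already scheduled every other cycle, but the team should confirm that the case report form lets absence of suspected relapse be derived at each visit. The downside is that a relapse with no blood or clinical sign is dated late, which makes RFS slightly optimistic.
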